Cover Page

Title: Improving Social Interaction for Adolescents with Autism During the Transition to Adulthood

NCT Number: NCT03785327

Document Date: 7/2018

Methodology

Participants

In total, we are aiming for 154 participants ages 18 to 21 to be tested interacting in pairs of one autistic and one non-autistic participant. Participants are assigned to one of three conditions:

1. The “neurostimulation” group with 22 autistic and 44 non-autistic adolescents. The autistic participants complete two sessions with different non-autistic participants at least one week apart, once with active neurostimulation preceding the social interaction, and once with sham neurostimulation in order to rule out placebo effects. This group allows for evaluation of Goal 2.
2. The “inclusion training” group with 22 autistic and 22 TD adolescents. Each non-autistic participant receives inclusion training prior to the interaction. Comparing outcomes with the “no intervention” group allows for evaluation of Goal 3.
3. The “no intervention” group consists of 22 autistic and 22 non-autistic adolescents. This group allows for evaluation of Goal 1 and also serves as a baseline for comparison with the intervention groups.

All participants will be male and between 18 and 21 years old. There is a disproportionate male to female ratio in autism of 4:1 (Fombonne, 2009), and the recruitment source used for this study is over 80% male. Thus, we would not have enough female participants to assess gender effects and because social interaction likely differs between mixed-sex interactions relative to same-sex ones, including a handful of females would confound reported findings. All included autistic participants will have a composite score above the clinical threshold for ASD on the Autism Diagnostic Observation Schedule (ADOS-II; Lord et al., 2012). Non-autistic participants will have no history of psychiatric illness or developmental disabilities and no current ASD diagnosis or a first degree relative with an ASD diagnosis. Interaction partners within and across the three groups will be matched on age and race, and comparable on IQ. To control for effects of intellectual ability, and to ensure results are most relevant to autistic older adolescents without intellectual disability, all participants will have measured full-scale IQs over 80 to ensure they are in the average to above average range.

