1. *The Social Interaction Evaluation Measure* (Berry & Hansen, 1996): assesses each partners' evaluation of interaction quality (e.g., enjoyment of the interaction), disclosure (e.g., how much did your partner disclose in the conversation), engagement (e.g., how much did your partner influence the conversation), and intimacy (e.g., to what extent was the interaction intimate).
2. *First Impression Scale* (Sasson et al., 2017): participants rate their partner on different traits (e.g., likeability and intelligence) and their intent to engage in future interactions.
3. *The Subjective Closeness Index* (Berscheid et al., 1989) and *the Inclusion of the Other in the Self* (Aron et al., 1997): participants rate feelings of "closeness" to their partner, which is predictive of friendship formation of two unfamiliar partners and can be reliably detected even in brief interactions (Aron et al., 1997).

For items 1 and 2 above, participants will also report how they expect they will be rated on these items by their partner. We have shown that young autistic adults are often less accurate at determining how they are viewed by others (Sasson et al., 2018), an important skill for managing social relationships. We predict here that older autistic adolescents will not only be rated more poorly by their non-autistic partner than vice versa, but that they also will be poor at detecting they are being evaluated in this way. The neurostimulation intervention that targets areas of the brain involved in perspective-taking is predicted to improve this ability in our autistic participants. In contrast, the inclusion training is predicted to improve non-autistic impressions of autistic participants, but not affect autistic behavior or responses.

Participants also complete measures assessing their social cognitive and social motivation abilities, as these affect social behavior and often differ in autism:

1. *Penn Emotion Recognition Task* (Kohler et al., 2000): assesses the ability to recognize five basic emotions (i.e., happiness, sadness, fear, anger, and no emotion) from facial expressions.
2. *Benton Facial Recognition Task* (Benton et al., 1983): measures the ability to process facial identity.

3. *The Awareness of Social Inference Task* (TASIT; MacDonald et al., 2003): participants will view 16 videotaped vignettes of social interactions involving white lies or sarcasm and are asked to answer questions about what the characters' intentions and motivations.

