All analyses addressing each of the three goals will be conducted separately for each social interaction outcome: social interaction evaluation, closeness, and first impressions formed (i.e., traits and behavioral intentions). Analyses for goal 3 (the “no intervention” condition) will serve as a baseline to compare effectiveness of the neurostimulation intervention (goal 1) and the inclusion training (goal 2). Compared to baseline, it is anticipated that neurostimulation of autistic participants will lead to increased evaluation of their social skill, better performance on social cognitive tasks, and higher ratings by their non-autistic partners on closeness and first impressions. Both partners in the neurostimulation condition are predicted to rate the quality of the social interaction higher than in the baseline condition. Goal 2 (inclusion training for the non-autistic participant) is predicted to lead to higher ratings of closeness and first impressions made by non-autistic participants of their autistic partners, with both partners evaluating the social interaction more positively compared to the “no intervention” condition. Because inclusion training only targets the non-autistic individual, social skill and social cognitive performance of autistic participants is not expected to differ here compared to baseline. Finally, we will be able to compare effects between Goal 1 and Goal 2 to determine which intervention, neurostimulation or inclusion training, produces better social outcomes for autistic adolescents. Due to the number of tests that will be performed, all significance tests will be evaluated at an adjusted alpha threshold of .01.

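### The neurostimulation hypotheses are set against a no-intervention group with no described second session, and the sham session has no analytic role, so placebo response and possible repeat exposure are not separated from stimulation

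*Combined protocol and SAP*

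**What the plan says.** **Design (Methodology, Participants).** For the 22 autistic members of the neurostimulation group, "The autistic participants complete two sessions with different non-autistic participants at least one week apart". The two sessions differ in stimulation: "once with active neurostimulation preceding the social interaction, and once with sham neurostimulation in order to rule out placebo effects". No rule is given for which comes first. For the comparator, "The “no intervention” group consists of 22 autistic and 22 non-autistic adolescents", and this group "also serves as a baseline for comparison with the intervention groups". No second session is described for it, nor for the inclusion training group.

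**Analysis (Analytic Plan).** The closing paragraph identifies the no-intervention condition as the baseline and then predicts, in comparison with it, that "neurostimulation of autistic participants will lead to increased evaluation of their social skill, better performance on social cognitive tasks", along with higher partner ratings. It also plans to compare neurostimulation with inclusion training. The model is an Actor Partner Interdependence Model with actor, partner and interaction effects. The mixed ANOVAs concern the training question only. The word sham does not occur in the Analytic Plan, and no session, period or order term is listed.

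**Tasks (Measures).** The social cognitive battery covers emotion recognition, face recognition and a social inference task in which "participants will view 16 videotaped vignettes of social interactions involving white lies or sarcasm". The section does not say at which session the battery is given, whether it is repeated, or whether alternate forms exist.

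**The concern.** A sham session is costly. It needs a second visit for each autistic participant and 22 additional partners. Its stated purpose is to exclude placebo effects, and it can do so only if active is compared with sham. The contrast written into the hypotheses compares active stimulation with people who had no device session at all, so any response to the procedure itself counts as a stimulation effect.

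The same contrast is also unequal in exposure. Any participant whose active session comes second has already been through the conversation procedure once, and perhaps the task battery too. A gain from repetition would then be read as a gain from stimulation. The comparison of neurostimulation with inclusion training has the same imbalance.

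**Working it through.** **Inputs from the documents.** 22 autistic participants per group; two sessions in the neurostimulation group; one described session in the no-intervention group; alpha .01. The stated total reproduces: (22 + 44) + (22 + 22) + (22 + 22) = 154. The 44 partners for 22 autistic participants confirm two dyads per person.

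**Assumptions, not in the documents.** Practice gain p = 0.2 to 0.5 SD at a second administration; tasks given at both sessions; two-sided tests; no true stimulation or placebo effect; SD of 1 in both groups; within-person correlation 0.5 for the active vs sham line. The plan gives no figure from which a placebo response could be sized, so none is calculated.

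**Bias.** Let w be the share of participants whose active session is second.

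- Active mean = w × p above a first-exposure mean. Sham mean = (1 − w) × p above it. No-intervention mean = 0 above it.
- Active minus no-intervention: bias = w × p.
- Active minus sham: bias = w × p − (1 − w) × p = (2w − 1) × p.

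**False-positive rate, active vs no-intervention.** Noncentral t with 22 + 22 − 2 = 42 degrees of freedom and noncentrality bias × √(22/2) = bias × √11. The nominal rate is 1%.

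| Order | w | Bias at p = 0.2 | Rejection | Bias at p = 0.5 | Rejection |
|---|---|---|---|---|---|
| Active always first | 0 | 0 | 1.0% | 0 | 1.0% |
| Balanced | 0.5 | 0.10 SD | 1.4% | 0.25 SD | 3.8% |
| Active always second | 1 | 0.20 SD | 2.7% | 0.50 SD | 16.3% |

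If the anticipated medium effect is taken as 0.5 SD (the plan gives no number), the balanced-order bias is 0.10/0.5 = 20% to 0.25/0.5 = 50% of it.

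**Active vs sham.** With balanced order the bias is (2 × 0.5 − 1) × p = 0. With active always second it is +p, and with active always first it is −p. In either unbalanced case the test rejects 4.4% (p = 0.2) to 34.0% (p = 0.5) of the time at a nominal 1%.

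Balanced order therefore clears the active vs sham contrast but leaves half the practice gain in active vs no-intervention. Putting active first for everyone removes practice from the second contrast only by biasing the first against stimulation.

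**The case against.** The strongest reply is that the practice argument depends on facts the documents do not give.

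- **Repetition is not stated.** The Measures section says the battery is completed, not when or how often. A single administration in the active session could support the prediction against baseline, and item practice would then be nil. This stands: the practice figures are conditional.
- **Order is not stated.** A reader might infer that order was unbalanced, or that the bias must favour the hypothesis. The documents support neither. They are silent on order, and if active always came first the practice bias against baseline is zero.
- **Sham does have a stated purpose.** The Participants section ties it to excluding placebo effects, which implies an active vs sham comparison. That is a fair reading of the design. But the Analytic Plan never makes that comparison and frames every neurostimulation prediction against the no-intervention group, so the two sections do not agree on which contrast tests stimulation.
- **Partner ratings are largely protected.** Each session uses a new non-autistic partner, so closeness and first-impression ratings by partners come from first-time raters. Repetition can reach them only through the autistic participant's familiarity with the procedure. This stands, and the assumed 0.2 to 0.5 SD should not be carried over to those outcomes.

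One reply does not stand: that counterbalancing settles the matter. It does so for active vs sham. Against the no-intervention group, half of the active sessions would still be second sessions.

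**Conclusion.** The concern holds in a limited form. As written, the contrast that carries the neurostimulation hypotheses cannot distinguish stimulation from placebo response or, for participants who receive active second, from repeat exposure. The sham data that could make the distinction have no place in the analysis. The placebo part does not depend on order or on whether the tasks are repeated.

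The practice part is conditional on both. Under the assumed gains, the inflation is slight to moderate with balanced order and material only towards the upper end with active always second; the 16.3% figure needs the largest assumed gain and the worst order together. The risk is greatest for the social cognitive tasks. It would be going too far to say that practice has been shown to contaminate the result. The documents show that the plan could not detect or remove it. This should be corrected.

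**What to change.** 1. State that active/sham order is randomised in equal numbers, 11 and 11.
2. Name the within-person active vs sham contrast as the test of stimulation. Fit it with a fixed effect for session (first or second) and a random effect for the autistic participant, since each appears in two dyads.
3. State whether the social cognitive tasks are given at both sessions and, if at only one, which.
4. Treat active vs no-intervention, and active vs inclusion training, as supportive. Use the session-adjusted estimate, say that it assumes no carryover from the first session to the second, and add a sensitivity analysis restricted to first sessions.

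**Cost.** An order list, one fixed effect and one random effect. If testing is already complete, order cannot be changed, but the session term and the first-session analysis need only the session dates. The first-session analysis compares about 11 with 22. For an assumed 0.5 SD effect the noncentrality is 0.5 × √(11 × 22/33) = 1.35 on 31 degrees of freedom, giving about 10% power at two-sided .01. It can serve as a check on direction, not as a test.

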4. *Friendship Motivation Scale* (Richard & Schneider. 2005): a 12-item questionnaire that assesses the participant's desire to seek out and form social relationships.

Analytic Plan

Sample sizes were selected in consultation with Statistician [name] to ensure successful detection of the anticipated medium effect sizes with 80% power. The research team consists of established researchers who are well experienced in data analysis and interpretation. For this project, we have selected an analytic approach designed to evaluate our three primary research goals. First, all self-report questionnaires will be evaluated for internal consistency using Cronbach's alpha, and the Conversation Probe social behaviors will be evaluated with Intraclass Correlation Coefficients (ICC) for agreement between coders. In addition to reliability, descriptive statistics will be run for all measures, examining group means, standard deviations, and normality of all measures.

Next, all primary goals will be assessed using an "Actor Partner Interdependence Model" (APIM; Kenny, Kashy, and Cook, 2006). Because data will be collected on two interacting individuals, the primary outcomes for both partners will be related (i.e., interaction evaluations, closeness, and impressions are dependent on the interaction with the partner). Thus, outcomes will be non-independent, and traditional analytic techniques using the general linear model cannot be used. Additionally, hypotheses examining how the partners influence each other cannot be examined with these traditional techniques and instead must be modeled with analyses like the APIM that take non-independence into account. APIM can estimate three types of effects. First, APIM can specify actor effects, or the effect of the individual's own behavior (e.g., overall social skills or social cognitive ability) on the individual's own outcome (e.g., interaction quality). Second, these models can specify partner effects, or the effect of the partner's behaviors or abilities on the individual's outcome. Finally, this model can specify interaction effects, allowing for examination of how an individual's behaviors and traits are related to his own outcomes depending on his partner's behaviors and traits.

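### The plan promises to find which of two interventions is better, but the head-to-head contrast is not defined and, with 22 per group at alpha .01, is far below 80% power

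*Combined protocol and SAP*

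**What the plan says.** The last paragraph of the Analytic Plan states, as something the trial will be in a position to do, that effects for Goal 1 and Goal 2 will be compared "to determine which intervention, neurostimulation or inclusion training, produces better social outcomes for autistic adolescents". Its next sentence adds that "all significance tests will be evaluated at an adjusted alpha threshold of .01". No contrast, outcome, rater, test or power is given for this comparison. The only power statement, earlier in the Analytic Plan, is general: sample sizes were chosen "to ensure successful detection of the anticipated medium effect sizes with 80% power", with no test, alpha or numerical effect size attached.

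The Participants section describes a neurostimulation "group with 22 autistic and 44 non-autistic adolescents", an inclusion training "group with 22 autistic and 22 TD adolescents", and a no-intervention group of 22 and 22. Autistic participants in the stimulation group attend twice, "once with active neurostimulation preceding the social interaction, and once with sham neurostimulation in order to rule out placebo effects". No sham or attention control is described for inclusion training, which is compared with no intervention.

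The last paragraph of the Analytic Plan then states the predictions for both interventions relative to the no-intervention group. The Participants section also calls that group a baseline for the intervention groups.

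The goal numbers differ. In Participants, no intervention is Goal 1, neurostimulation Goal 2 and training Goal 3. In the last paragraph of the Analytic Plan, neurostimulation is goal 1, training goal 2 and no intervention goal 3.

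**The concern.** Deciding which of two interventions is better needs a defined contrast and enough precision to separate them. The plan gives no contrast, and the precision follows from 22 against 22 at a strict alpha. If the comparison is reported as planned, the likeliest result is a non-significant one that says almost nothing about relative merit, while the plan tells readers that the question could be settled.

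The choice of comparator also changes what is compared. Sham was included to remove placebo response from the stimulation effect. If both interventions are instead judged against no intervention, that protection is not used. If each is judged by its own comparator in Participants, a sham-controlled within-person effect is set against a between-group effect with no control for expectation.

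**Working it through.** **Inputs from the documents.** 22 autistic participants per group (Participants); alpha .01 for all tests, medium effects and 80% power (Analytic Plan).

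**Assumptions, because the documents are silent.** Medium means d = 0.5 with SD 1; tests are two-sided; no dropout; session correlation r from 0 to .9; within-dyad correlation from 0 to .7.

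**1. The plan's 80%.** It is not tied to a test. For 22 vs 22 and d = 0.5, exact two-sample t power is 36.7% at .05 and 16.3% at .01. Figures near 80% appeared only at alpha .05 and with further unstated assumptions:
- all 154 people treated as independent in a three-group ANOVA, f = 0.25: 79.1%;
- a paired test with d = 0.5 and session correlation .7: 82.3%;
- a group-by-partner interaction, f = 0.25, 44 dyads, within-dyad correlation .3: 78.2%.

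At .01 these fall to about 57%, 58% and 55%. None of them is the head-to-head contrast.

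**2. Active stimulation vs training, one partner's score.** This is what remains when both are referred to the same no-intervention group.
- SE = √(2/22) = 0.3015 SD.
- Noncentrality = 0.5/0.3015 = 1.658; critical t (42 df) = 2.698.
- Power = 16.3% for a difference of 0.5 SD, 5.3% for 0.3 SD and 2.7% for 0.2 SD.
- Detectable difference at 80% power: 1.07 SD. For 0.5 SD, 96 per group would be needed.
- 99% confidence interval half-width: 2.698 × 0.3015 = 0.81 SD.

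**3. More efficient versions of the same contrast.** Averaging both partners' ratings multiplies the SE by √((1+ρ)/2), if the effect is 0.5 SD in each partner. A covariate multiplies it by √(1−R²).

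| Version | Power at .01 |
|---|---|
| Both partners, ρ = 0 / .3 / .5 / .7 | 37% / 27% / 23% / 20% |
| Covariate, R² = .10 / .25 / .50 | 18% / 23% / 37% |

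Stacking the two, for example ρ = .3 with R² = .50, gives about 59%.

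**4. (Active − sham) vs (training − none).** SE = √((2(1−r) + 2)/22), with 63 df (66 autistic participants less three groups).

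| r | SE | Power for 0.5 SD | Detectable difference, 80% power |
|---|---|---|---|
| 0 | 0.426 | 7.6% | 1.50 |
| .3 | 0.393 | 9.1% | 1.38 |
| .5 | 0.369 | 10.4% | 1.30 |
| .7 | 0.344 | 12.3% | 1.21 |
| .9 | 0.316 | 15.0% | 1.11 |

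With 42 df the detectable differences for r = .3 and .7 are 1.40 and 1.22, so about 1.2–1.4 SD across that range.

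**5. Ranking by point estimate.** If the true difference is 0.2 SD, the direct contrast has the wrong sign with probability Φ(−0.2/0.3015) = Φ(−0.663), about 25%.

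**6. Which contrast is meant.** Under the Participants numbering, Goal 1 against Goal 2 would be no intervention against neurostimulation. Under the later numbering it is neurostimulation against training. The sentence names the two interventions, so the intended pair can be recovered, but the comparator for each, the outcome and the rater cannot.

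**The case against.** The comparison is not one of the three goals. It is a closing remark, and the 80% statement is not attached to it. The same 22-vs-22 arithmetic applies to training against no intervention, so part of this is the trial's general power problem. An estimate with an interval will exist, however imprecise. All of that stands, and it is why the remedy is rewording and not a larger trial. It does not rescue the sentence, which says the trial can decide between the interventions.

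A reader might infer more than the documents support, in four ways.

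- **That 16% is a ceiling.** It is not. The planned actor–partner model uses both partners' data, and a covariate is described for the training ANOVAs, so 18–37% is plausible from either device alone. The pooled figures do assume an equal effect in both partners, and ρ = 0 conflicts with the plan's own premise that partners' outcomes are related.
- **That the expected difference is near zero because both effects are medium.** The plan does not give an effect size for each intervention. It predicts that stimulation, but not training, will improve autistic participants' social skill and social cognition. A small difference is plausible only on shared outcomes such as closeness and first impressions.
- **That the plan necessarily compares unlike effects.** This holds for the contrasts in Participants. Under the Analytic Plan both interventions share the no-intervention baseline, which cancels. Expectation effects then remain in both arms, and the two interventions still act on different members of the dyad.
- **That the plan will rank by point estimates or by which p-value passes .01.** It proposes neither. A bar on ranking is a precaution.

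**Conclusion.** The concern holds in this form: the plan claims a capability that the design does not have, for a contrast that it does not define. Even if one intervention has a medium effect and the other none, power at .01 is about 16% on one partner's score, about 18–37% with pooling or a covariate, and about 8–15% for the sham-controlled version with session correlation 0 to .9. The detectable differences are about 1.07 SD for the direct contrast and 1.2–1.4 SD for the sham-controlled one (session correlation .7 to .3), against an assumed medium effect of 0.5 SD.

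These figures rest on d = 0.5, two-sided testing and no dropout, none of which the documents state. The conclusion does not depend on the exact values: neither pooling nor a covariate alone exceeds about 37%, and the combination shown reaches only 59% while still assuming that one intervention does nothing. The sentence should be changed before results are reported.

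**What to change.** In the last paragraph of the Analytic Plan:

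1. Refer to the interventions by name instead of by goal number, and align the goal numbering with the Participants section.
2. Replace the sentence on deciding between the interventions with wording such as: the difference between active neurostimulation and inclusion training will be estimated, with a confidence interval, on [named outcome, named rater] as an exploratory analysis; no ranking of the interventions will be claimed from it.
3. Add active-minus-sham against training-minus-none as a sensitivity version, and say that expectation effects remain in both arms of the direct contrast and are uncontrolled for training in either version.
4. State the detectable differences (about 1.07 SD, and about 1.2–1.4 SD for the sensitivity version) with their assumptions.
5. State that one intervention passing .01 and the other not passing it is not evidence that they differ.

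The cost is a few sentences of analysis-plan text. No extra participants or procedures are needed. The downside is that the stated claim becomes less favourable.

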To examine effects of autism acceptance training on non-autistic participants interaction with autistic partners, zero-order correlations between participants' interaction ratings were evaluated to assess the relationship between indicators, as well as the consistency of ratings between partners. Two factor mixed-model ANOVAs were run using a Geisser-Greenhouse correction to assess the effects of diagnosis (autistic vs. non-autistic) and training condition (Autism Acceptance Training vs. control) on how participants evaluated their conversation partner and the overall interaction. Specifically, training condition was treated as a between-subjects variable and autistic and NA interaction ratings (interaction quality, first impressions, closeness, warmth and dominance) were treated as a within-subjects factor, with separate analyses run for each outcome measure. As IQ differed significantly between autistic and NA individuals within dyads, WRAT-3 scores were included as a covariate in each ANOVA. All analyses were completed using SPSS 27 (IBM SPSS Inc., 2015).

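### Does the .01 significance threshold need a stated test count, family and error target before it can stand?

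*Combined protocol and SAP*

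**What the plan says.** The last paragraph of the Analytic Plan sets the threshold: "Due to the number of tests that will be performed, all significance tests will be evaluated at an adjusted alpha threshold of .01". No number of tests, correction method or overall error rate appears there or elsewhere.

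The same paragraph has each goal analysed separately for three outcomes: "social interaction evaluation, closeness, and first impressions formed (i.e., traits and behavioral intentions"). The earlier Analytic Plan paragraph on the Actor Partner Interdependence Model (APIM) names the same three as the primary outcomes.

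The paragraph on autism acceptance training is in the past tense and uses five: "autistic and NA interaction ratings (interaction quality, first impressions, closeness, warmth and dominance) were treated as a within-subjects factor". It looks at two effects per outcome: "Two factor mixed-model ANOVAs were run using a Geisser-Greenhouse correction to assess the effects of diagnosis (autistic vs. non-autistic) and training condition". It states no alpha of its own.

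The Measures section describes what the instruments cover, for example "evaluation of interaction quality (e.g., enjoyment of the interaction), disclosure (e.g., how much did your partner disclose in the conversation), engagement" and intimacy for the evaluation measure. It adds expected ratings: "For items 1 and 2 above, participants will also report how they expect they will be rated on these items by their partner".

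Under Participants, the neurostimulation arm is tested twice, "once with active neurostimulation preceding the social interaction, and once with sham neurostimulation in order to rule out placebo effects", and is tied to a goal: "This group allows for evaluation of Goal 2". The closing paragraph of the Analytic Plan calls the same intervention goal 1.

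**The concern.** A threshold justified by the number of tests invites the question of how many tests there are, and the document does not answer it. The count depends on where one looks. There are three outcomes in two paragraphs of the Analytic Plan and five in the training paragraph. Splitting the instruments under Measures gives eight component scores (four evaluation dimensions, two parts of the impression scale, two closeness scales).

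The contrasts are open too: each intervention against baseline, one intervention against the other, active against sham, and autistic against non-autistic partners in the untreated dyads. The goal numbers differ between sections, so a family per goal is awkward to assign.

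If this mattered in full, a reader could not say what overall error rate lies behind a result at p < .01. The family could also be described after the results in whatever way made .01 look adequate.

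**Working it through.** **Inputs.** Per-test alpha .01, three outcomes or five, and two effects per training ANOVA come from the Analytic Plan. The 22 dyads in each of the training and no-intervention groups come from Participants. The family-wise target is not stated, so 5% is assumed, with 10% as the alternative.

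**Can .01 be reproduced?** Bonferroni gives target / m for m tests.
- At a 5% target: .05/3 = .0167, .05/5 = .0100, .05/9 = .0056, .05/10 = .0050. The only exact match is m = 5, which is the number of outcomes in the training paragraph. The text never makes that link.
- At a 10% target: .10/3 = .0333, .10/5 = .0200, .10/10 = .0100. The match moves to m = 10.

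**Overall error at .01 per test.** The ceiling is m × .01 whatever the correlation. With independent tests it is 1 − .99^m. The last column is a simulation of 60,000 null trials with 22 dyads per arm and two-sided t tests (mixed-ANOVA effects in the ten-test and last rows) standing in for the APIM. It assumes outcome correlation 0.3 / 0.5 / 0.7, within-dyad correlation 0.2, and correlation 0.3 between two partners' ratings of one autistic participant. The WRAT-3 covariate is left out.

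| Tests counted | m | .05/m | Ceiling | 1 − .99^m | Simulated |
|---|---|---|---|---|---|
| One contrast, 3 outcomes | 3 | .0167 | 3% | 3.0% | 2.9 / 2.7 / 2.5% |
| One contrast, 5 outcomes | 5 | .0100 | 5% | 4.9% | 4.7 / 4.2 / 3.7% |
| Two interventions v baseline, 3 outcomes | 6 | .0083 | 6% | 5.9% | 5.5 / 5.1 / 4.6% |
| One contrast, 8 component scores | 8 | .00625 | 8% | 7.7% | 7.1 / 6.3 / 5.0% |
| Three arm contrasts, 3 outcomes | 9 | .0056 | 9% | 8.6% | 7.7 / 7.0 / 6.5% |
| Diagnosis and training, 5 outcomes | 10 | .0050 | 10% | 9.6% | 9.0 / 8.3 / 7.2% |
| Five contrasts, 3 outcomes | 15 | .0033 | 15% | 14.0% | 12.4 / 11.5 / 10.4% |
| Diagnosis, training and their interaction, 5 outcomes | 15 | .0033 | 15% | 14.0% | 13.3 / 12.1 / 10.4% |

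A separate simulation of 40,000 null trials agreed within about 0.4 percentage points on every row except the five-contrast one, which it did not cover. Arm contrasts share groups and are not independent, so the 1 − .99^m column overstates those rows.

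**What .01 buys.** Nine independent tests at an unadjusted .05 would give 1 − .95^9 = 37.0%, and ten would give 1 − .95^10 = 40.1%. At .01 these fall to 8.6% and 9.6%.

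**Which list governs?** The two forward-looking paragraphs of the Analytic Plan agree on three outcomes. Only the account of the completed training analysis has five. Nowhere does the document list eight outcomes: that figure comes from dividing instruments into parts, and describing an instrument's dimensions is not a plan to test each one. Warmth and dominance are not named under Measures, but the impression scale's traits are given there only as examples, so their source cannot be determined. The outcome problem is therefore one discrepancy, three against five.

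**Does the count change a decision?** The rule covers all significance tests at .01. A p value of .008 passes and one of .02 fails, whether the family is called three, five or ten tests.

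**The case for a change.** The strongest reply is that the counts with most support in the text are not the lenient-looking small ones. The closing paragraph names three comparisons between arms, which with three outcomes makes nine tests. The training ANOVAs have at least ten. Both exceed 5% at .01. If all three APIM effect types were tested for three goals and three outcomes, the count would be 27, with a ceiling of 27% and 1 − .99^27 = 23.8%. A sponsor who gives the number of tests as the reason for .01 ought to be able to state that number. The training paragraph, written in the past tense with a different list and no alpha, is also where a family could be drawn after the fact.

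Much of this stands as description. The count, family and target are missing, the two lists do differ, and the goal numbers do not match.

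It does not show that .01 is wrong. Exceeding 5% is a fault only against a 5% target, and the plan sets none; at 10%, .01 is sufficient for up to ten tests. The 27-test figure treats what the APIM is able to estimate as a list of confirmatory tests. On its face the rule for all tests covers the training ANOVAs, and redescribing the family would change only the label on the error rate. Choosing which outcomes to report is a different risk, which a stated count would not remove. For analyses already run, a count written now would describe the error rate but could not restore pre-specification. The goal numbers are a slip: each intervention is identified by name wherever it is discussed.

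**Conclusion.** The gap is real but no change to the plan follows. The document fixes a single threshold five times stricter than .05 (.05/.01 = 5), applies it to every test, and so caps overall error at 1% per test counted. A reader who prefers another family can apply its divisor to the p values.

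If a 5% family-wise target is assumed, .01 suffices for up to five tests. On the nine-test reading the overall error is about 6.5% to 7.7%, and on the ten-test reading about 7.2% to 9.0%. These ranges rest on outcome correlations of 0.3 to 0.7, on simple t and ANOVA tests in place of the APIM, and on the other assumed correlations given with the table. The ceilings of 9% and 10% do not depend on the correlations.

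Writing down the count, the family and the target would make the rationale easier to follow but would leave the threshold and every test decision where they are. The three-against-five outcome lists and the goal numbers are matters of clerical reconciliation. Whether 22 dyads per group give adequate power at .01 is a separate question that this point does not settle.
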